##### *Morphology Findings*

New ECG morphologies for each participant not present on any ECG at baseline for that participant will be summarized for all observation time points combined.

The number and percentage of participants having T-wave morphology changes and/or the occurrence of abnormal U-waves that represent the appearance or worsening of the morphological abnormality from baseline will be reported.

### *Concentration-QTc Analyses*

A concentration-QTc regression analysis, based on data collected from the ECG recordings after drug administration and concentration values for each participant at each matching time point, will be performed. The concentration-ECG relationship will be first evaluated by some descriptive plots to investigate any potential delayed or sustained effects and explore the shape of the relationship. Then, linear or nonlinear models will be implemented to estimate the slope and 95% confidence interval of the relationship. Predictions at selected concentration values will be computed within the model.

#### 12.4.8.3 Laboratory Data

The summary statistics (including number, mean, median, SD, minimum, and maximum) of all laboratory variables (laboratory values and changes from baseline), will be calculated for each visit (baseline and post-baseline time points) and presented by treatment group.

Listings of participants with laboratory values that are out of the reference range will be produced.

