performed >6 months prior to Screening may be enrolled if study eligibility criteria for LVOT gradient criteria are met)

14. ICD placement or pulse generator change within 2 months prior to Screening or planned new ICD placement during the study (pulse generator changes, if needed during the study, are allowed)
15. Has QT interval with Fridericia correction (QTcF) >500 ms at Screening or any other ECG abnormality considered by the investigator to pose a risk to participant safety (eg, second-degree atrioventricular block type II)
16. Has documented obstructive coronary artery disease (>70% stenosis in one or more epicardial coronary arteries) or history of myocardial infarction
17. Has known moderate or severe (as per investigator's judgment) aortic valve stenosis at Screening
18. Has any acute or serious comorbid condition (eg, major infection or hematologic, renal, metabolic, gastrointestinal, or endocrine dysfunction) that, in the judgment of the investigator, could lead to premature termination of study participation or interfere with the measurement or interpretation of the efficacy and safety assessments in the study
19. Has pulmonary disease that limits exercise capacity or systemic arterial oxygen saturation
20. History of malignant disease within 10 years of Screening:
  - Participants who have been successfully treated for nonmetastatic cutaneous squamous cell or basal cell carcinoma or have been adequately treated for cervical carcinoma in situ or breast ductal carcinoma in situ (DCIS) can be included in the study
  - Participants with other malignancies who are cancer-free for more than 10 years before Screening can be included in the study
21. Has safety laboratory parameters (chemistry, hematology, coagulation, and urinalysis) outside normal limits (according to the central laboratory reference range) at Screening as assessed by the central laboratory; however, a participant with safety laboratory parameters outside normal limits may be included if he or she meets all of the following criteria:
  - The safety laboratory parameter outside normal limits is considered by the investigator to be clinically not significant
  - If there is an alanine aminotransferase or aspartate aminotransferase result, the value must be  $<3 \times$  the upper limit of the laboratory reference range
  - The body size-adjusted estimated glomerular filtration rate is  $\geq 30 \text{ mL/min}/1.73 \text{ m}^2$

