## 12.2.5 Safety Endpoints

- Incidence of major adverse cardiac events (death, stroke, acute myocardial infarction)
- Incidence of hospitalizations (both cardiovascular (CV) and non-CV))
- Incidence of heart failure (HF) events, (includes HF hospitalizations and urgent emergency room (ER)/outpatient (OP) visits for HF)
- Incidence of atrial fibrillation/flutter (new from screening)
- Incidence of ICD therapy and resuscitated cardiac arrest
- Incidence of Ventricular tachyarrhythmias (includes VT, VF, and Torsades de Pointe)
- Incidence of syncope and seizures
- Frequency and severity of treatment-emergent adverse events (TEAE), treatment-emergent SAEs, and laboratory abnormalities (including trends in NT-proBNP)

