#### 12.4.8 Safety Analyses

All safety analyses will be performed on the Safety Population using the following common rules:

- The baseline value is defined as the last available value before the first administration of study drug
- For quantitative safety parameters based on central laboratory measurements, descriptive statistics will be used to summarize results and change from baseline values by visit and treatment group; resulting changes may be presented in shift tables or scattergrams
- The analysis of the safety variables will be descriptive and no hypothesis testing is planned

The safety analysis will focus on the treatment-emergent period, which is defined as the time from the first administration of study drug to the last administration of study drug + 56 days.

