6. GENERAL STATISTICAL CONSIDERATIONS

The primary analysis will be conducted through the 30-week treatment period. Data collected through this time point will be cleaned and locked prior to conducting the primary analysis.

Once all participants have completed their Week 38/end of study (EOS) visit, all data will be cleaned and locked, and analyses using this data will be used to inform study objectives relating to follow-up safety and reversibility of drug effect.

SAS® version 9.4 or higher will be used for statistical analyses, tabulations, and graphical presentations.

In general, descriptive summaries will be presented by treatment group (placebo and mavacamten) for values at each visit. The descriptive summary for continuous variables will also be provided for the change from baseline and, if appropriate, for the change from week 30 to week 38. Summaries of continuous variables will include the number of subjects (N), mean, standard deviation (SD), median, Q1, Q3, minimum, and maximum. For variables with highly skewed distribution (e.g. log-normal distribution), geometric mean and %CV will also be reported in descriptive summaries. Inferential analysis for those variables may be performed after log-transformation as deemed appropriate. Descriptive summaries for categorical variables will include the number and percentage of subjects. Unless otherwise stated, denominators for percentages will be the number of subjects in the analysis population.

Between-group comparisons will focus on the comparative performance of mavacamten versus placebo. All statistical tests will be conducted at a 2-sided significance level of 0.05.

In general, baseline is defined as the last nonmissing value on or before the first dose date and time (as applicable). For certain data types (eg, accelerometer, PROs, cardiac rhythm monitoring, etc.), special considerations may be required. Refer to the specific data section for details.

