10.3. Safety Laboratory Data

Safety laboratory data will be summarized by treatment group and visit using descriptive statistics.

Shift tables reflecting changes from baseline (ie, normal to low, high, etc.) will be presented in lieu of descriptive statistics of changes from baseline. Listings of laboratory values will be generated and the results that are out of the reference range will be flagged.

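### SAP 10.3 replaces the change-from-baseline laboratory statistics that the protocol commits to with low/normal/high shift tables, so within-participant change is not summarised by arm

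*Protocol*

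**What the plan says.** The protocol makes the commitment twice. Section 12.4.8 says that for quantitative safety parameters measured centrally "descriptive statistics will be used to summarize results and change from baseline values by visit and treatment group". Section 12.4.8.3 says that summary statistics (number, mean, median, SD, minimum and maximum) "of all laboratory variables (laboratory values and changes from baseline), will be calculated for each visit", by arm. Shift tables are an optional extra in the protocol: "resulting changes may be presented in shift tables or scattergrams".

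The SAP's general rule in Section 6 agrees: "The descriptive summary for continuous variables will also be provided for the change from baseline". SAP 10.3 departs from it. It keeps descriptive statistics of laboratory values by arm and visit, and listings of laboratory values with out-of-range results flagged. For change, however, it says that shift tables between reference-range categories "will be presented in lieu of descriptive statistics of changes from baseline". ECG parameters (SAP 10.2.2) and vital signs (SAP 10.4) keep their change-from-baseline summaries.

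Exclusion criterion 21 (Protocol 5.3) allows entry with abnormal results: "a participant with safety laboratory parameters outside normal limits may be included if he or she meets all of the following criteria". The conditions are that the investigator judges the abnormality not clinically significant, that any ALT or AST is below 3 x ULN, and that eGFR is at least 30 mL/min/1.73 m².

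**The concern.** A shift table with low, normal and high categories registers only the crossing of a reference limit. A participant who enters with a high creatinine or CPK and then rises further stays in the high-to-high cell, however large the rise. A participant who moves a long way inside the range stays in normal-to-normal.

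The protocol's safety endpoints include the severity of laboratory abnormalities as well as their frequency, and the shift table carries no severity. Without change statistics, no visible table shows by arm how far individuals moved from their own starting point. For non-liver tests the visible SAP has no graded table that would fill the gap.

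**Working it through.** **1. Texts side by side.**

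| Display, by visit and arm | Protocol 12.4.8 / 12.4.8.3 | SAP 10.3 |
|---|---|---|
| Statistics of values | yes | yes |
| Statistics of change from baseline | yes | replaced |
| Shift tables | optional | yes |
| Listings | participants with out-of-range values | laboratory values, out-of-range flagged |

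The plan states no figure on this point, so there is none to reproduce.

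**2. What the shift table registers.** This is an illustrative simulation. The assumptions are not from the documents: a standard-normal analyte, reference limits at ±1.96 SD, a uniform upward drift, and r between 0.5 and 0.9. Among participants normal at baseline, 93% to 97% stay in normal-to-normal at a drift of 0.25 to 0.5 SD, and 84% to 85% at 1.0 SD. The shift table on its own therefore hides most within-range movement.

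**3. What the retained value summaries recover.** With complete data, follow-up mean minus baseline mean equals mean change. The simulation confirms this in every setting (0.25, 0.50 and 1.00 SD). The SD, minimum and maximum of change cannot be recovered from the visit tables, because they depend on the pairing. When visits are missed, the two visit means describe different participants and the subtraction is no longer exact.

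**4. Precision.** Let the analyte SD be 1 at each visit, with n = 110 per arm (Protocol 12.1).

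- SE of the between-arm difference in follow-up means: sqrt(2/110) = 0.135.
- SE of the between-arm difference in mean change: sqrt(2 × 2(1 − r)/110), which is 0.135 at r = 0.5, 0.104 at r = 0.7 and 0.085 at r = 0.8.
- Ratio of the first to the second: sqrt(1/(2(1 − r))) = 1.0, 1.29 and 1.58.

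| Drift | Raw follow-up means | Change, r = 0.5 | Change, r = 0.7 | Change, r = 0.8 |
|---|---|---|---|---|
| 0.5 SD | 0.5/0.135 = 3.7 SE | 3.7 SE | 0.5/0.104 = 4.8 SE | 0.5/0.085 = 5.9 SE |
| 0.3 SD | 2.2 SE | 2.2 SE | 2.9 SE | 3.5 SE |

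At r = 0.5 nothing is gained, and below 0.5 raw means are the more precise.

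**5. Liver tests below 3 x ULN.** Take an ALT or AST that rises from 1.2 to 2.9 x ULN. In the shift table it stays high-to-high. The elevation table in SAP 10.3.1 starts above 3 x ULN for ALT and AST, so it is not counted there. The protocol's maximum-elevation categories included a 1–3 x ULN band, which the SAP table lacks. The plot of peak ALT against peak bilirubin would show the ALT value but not its baseline, and it does not show AST.

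**The case against.** The strongest reply is that little is hidden. SAP 10.3 keeps by-visit statistics by arm, which under Section 6 include quartiles, minimum and maximum. It also lists the laboratory values. SAP 10.3.1 adds, for liver tests, counts by multiples of ULN, normalization judged against baseline where baseline exceeds ULN, and a Hy's law summary. Protocol 11.1.1 requires clinically important abnormalities that suggest new or worsening toxicity to be captured as adverse events, and SAP 10.1 tabulates these by severity. Protocol 12.4 calls its analyses an outline, the Section 6 rule is qualified as general, and safety is descriptive throughout. A mean change also does not isolate participants who were abnormal at baseline.

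Most of this stands, and it rules out some stronger readings. A reader might infer that drift and worsening are not shown at all. They are: drift in the visit means and individual worsening in the listings.

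A reader might also set limit crossings against mean change. At a 0.5 SD drift the expected numbers above the ULN are 2.7 and 7.9 of 110, a difference of 1.6 SE, against 4.8 SE for change at r = 0.7. That treats the shift table as the only display left. The fair comparator is the retained raw mean, at 3.7 SE.

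The reply does not justify the substitution. An outline leaves room for added detail, but SAP 10.3 removes a statistic that the protocol names twice and that the SAP keeps for ECG and vital signs. The adverse event route depends on investigator judgement and does not summarise change. Minimum and maximum change would at least expose the extreme individual movements that a category table and unpaired values do not.

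**Conclusion.** The departure is real and its consequence is modest. SAP 10.3 drops the paired change-from-baseline summary by visit and arm. Within-participant change, including worsening from an abnormal baseline and ALT/AST rises below 3 x ULN, is then not summarised by arm, chiefly for non-liver tests. In precision terms, the raw means that remain have a standard error 1.0 to 1.58 times that of changes for r from 0.5 to 0.8. These correlations and the drifts are assumptions; the documents give neither.

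No hypothesis test or efficacy result is touched. Two further inferences are not supported. The departure cannot be called undocumented, because SAP Section 14 is headed as a summary of changes to the protocol's planned analyses and its content is not visible in this copy. Nor can it be said that NT-proBNP or troponin changes go unanalysed: both have their own analysis windows in SAP Appendix 2 and may be covered in blacked-out text. This is a low-priority improvement.

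**What to change.** In SAP 10.3, change *in lieu of* to *in addition to*. Present n, mean, SD, median, minimum and maximum of change from baseline by visit and arm, as Protocol 12.4.8.3 states, and keep the shift tables. The cost is one phrase in the SAP and a block of change columns in by-visit tables that are already planned. No new data are needed.

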### *Potential Drug-induced Liver Injury*

The liver function tests, namely ALT, AST, ALP, and TBL, are used to assess possible drug-induced liver toxicity.

A graph of distribution of peak values of ALT versus peak values of TBL will be presented. Note that the ALT and TBL values are presented on a logarithmic scale. The graph will be divided into 4 quadrants with a vertical line corresponding to  $3 \times \text{ULN}$  for ALT and a horizontal line corresponding to  $2 \times \text{ULN}$  for TBL.

The normalization (to  $\leq 1 \times \text{ULN}$  or return to baseline if baseline  $>\text{ULN}$ ) of elevated liver function tests will be summarized by categories of elevation ( $3 \times \text{ULN}$ ,  $5 \times \text{ULN}$ ,  $10 \times \text{ULN}$ ,  $20 \times \text{ULN}$  for ALT and AST,  $1.5 \times \text{ULN}$  for ALP, and  $1.5 \times \text{ULN}$  and  $2 \times \text{ULN}$  for TBL), with the following categories of normalization: never normalized, normalized after permanent discontinuation of study drug. Note that a participant will be counted only under the maximum elevation category ( $1-3 \times \text{ULN}$ ,  $3-5 \times \text{ULN}$ ,  $5-10 \times \text{ULN}$ ,  $10-20 \times \text{ULN}$ ,  $>20 \times \text{ULN}$ ).

#### 12.4.8.4 Vital Signs Data

The summary statistics (including number, mean, median, SD, minimum, and maximum) of all vital sign variables (values and changes from baseline), will be calculated for each visit (baseline and post-baseline time points) and presented by treatment group.

Listings of participants with vital signs values that are out of the reference range will be produced.

#### 12.4.8.5 Other Safety Analyses

Abnormal physical examination results will be listed. Concomitant medications will be summarized.

[REDACTED]

[REDACTED]

[REDACTED]

[REDACTED]

[REDACTED]

[REDACTED]

[REDACTED]

[REDACTED]

[REDACTED]

#### 12.4.10 *Interim Analysis*

No interim analysis is planned.

[REDACTED]

[REDACTED]

[REDACTED]

[REDACTED]

### 13 STUDY COMPLIANCE AND ETHICAL CONSIDERATIONS

#### 13.1 Compliance Statement

This study will be conducted in accordance with the International Council for Harmonisation of Technical Requirements for Pharmaceuticals for Human Use (ICH) Good Clinical Practice (GCP) Guidelines; US Title 21 Code of Federal Regulations (CFR) Parts 11, 50, 54, 56, and 312; European Union (EU) GCP; cGMP; the principles enunciated in the Declaration of Helsinki; and all human clinical research regulations in the countries where the study is to be conducted.

#### 13.2 Informed Consent

The ICFs used for the study must comply with the Declaration of Helsinki, US 21 CFR Part 50, ICH GCP guidelines, and any other local regulations. The investigator, or a person delegated by the investigator, must explain the medical aspects of the study including the nature of the study and the treatment, orally and in writing, in such a manner that the potential participant is aware of potential benefits and risks. Potential participants must be informed that participation is voluntary and that they may withdraw from the study at any time, without prejudice. Participants, or a legal guardian if the participant is unable to, must give informed consent in writing.

Prior to participation in any study-related procedures, participants must sign and date an EC-approved written ICF in a language the participant can understand. The informed consent

process must be conducted, documented in the source document (including the date), and the form must be signed before the participant undergoes any study-specific procedures.

The language in the written information about the study should be as nontechnical as practical and should be understandable to the potential participant. Before informed consent is obtained, the investigator should provide the potential participant ample time and opportunity to inquire about the study and to decide whether or not to participate.

All questions about the study should be answered to the satisfaction of the participant. The written ICF should be signed and personally dated by the participant and by the person who conducts the informed consent discussion. All participants will receive a copy of his/her signed and dated ICF.

### **13.3            Ethics Committee**

The term EC used in this document refers to an Institutional Review Board (IRB) or Independent Ethics Committee (IEC) or equivalent. The EC must review and, if appropriate, approve the following documents, as applicable:

- Study protocol and amendment(s)
- Written ICF(s) and consent form updates
- Participant recruitment procedures/documents (eg, advertisements)
- Written information to be provided to participants
- IB and available safety information (Note: ECs do not approve IBs but are responsible for acknowledging receipt)
- Information about payments and compensation available to participants

The EC approval must be in writing, clearly identifying the study (by protocol date and/or version), the documents reviewed, including informed consent, and date of the review. The investigator has the responsibility to provide MyoKardia with the written EC approval prior to initiating any study-related procedures.

The investigator also has the responsibility to inform the EC of the following according to the EC's policy:

- All SUSARs (as described in [Section 11.3](#))
- Any new information that may affect adversely the safety of the participants or the conduct of the trial
- Protocol deviations
- A synopsis of the study report upon study completion

Documentation of subsequent reviews of the study must also be forwarded to MyoKardia.

## **14 ADMINISTRATIVE PROCEDURES**

### **14.1 Sponsor's Responsibilities**

MyoKardia reserves the right to terminate the study at any time. MyoKardia and the investigators will assure that adequate consideration is given to the protection of the participants' interests. MyoKardia retains the right to terminate the study and remove all study materials from a clinical site at any time. Specific circumstances that may precipitate such termination are:

- Request by Health Authority to terminate the study
- Unsatisfactory participant enrollment with regard to quality or quantity
- Significant or numerous deviations from study protocol requirements, such as failures to perform required evaluations on participants, maintain adequate study records or inaccurate, incomplete, or late data recording on a recurrent basis
- The incident or severity of AEs in this or other studies indicating potential health hazard caused by the study treatment

#### **14.1.1 *Participant Confidentiality***

The processing of personal data in pursuit of this study will be limited to those data that are reasonably necessary to investigate the utility of the study medications used in this study. These data will be processed with adequate precautions to ensure confidentiality according to applicable laws.

MyoKardia ensures that the personal data are:

- Collected for a specified and legitimate purpose
- Processed fairly and lawfully
- Accurate and up to date

Explicit consent for the processing of personal data will be obtained prospectively from the participating participant.

MyoKardia, whose responsibilities require access to personal data, agrees to keep the identity of participants confidential. This confidentiality will be maintained throughout the complete data processing.

Participants will be entitled to request confirmation of the existence of personal data held by MyoKardia and will have the right to rectify erroneous or inaccurate data up until database lock.

A series of 15 horizontal black bars of varying lengths, arranged vertically from top to bottom. The bars are positioned in a staggered pattern, with some bars appearing above and below others. The lengths of the bars decrease as they move down the page.

### **14.1.3                    *Investigator Training***

All clinical sites will have a center-specific study initiation meeting to ensure the center staff understands the protocol, study requirements and procedures, and data capture processes. This training will take place before the first participant is enrolled. Each clinical site will be provided with information regarding GCP and regulations specific to the conduct of the clinical studies. Each clinical site will be responsible for ensuring that new team members are adequately trained and the training is documented.

